**5.6.9. Slit Lamp Biomicroscopy**

Biomicroscopy will be performed in each eye at each visit, by slit lamp examination, without pupil dilation, including but not limited to lids/lashes, conjunctiva, cornea, and anterior chamber. Observations for the examination will be graded on a 5-point scale (0=none, 0.5=trace, 1=mild, 2=moderate, 3=severe) except for the anterior chamber (in cells: 0=0 cells, +0.5=1-5 cells, +1=6-15 cells, +2=16-25 cells, +3=26-50 cells, and +4=>50 cells; in flare: 0=none, +1=faint, +2=moderate, +3= marked and +4=intense).

The number and percentage of participants with clinically significant biomicroscopy findings will be tabulated by finding category, assessment timepoint and treatment group. A clinically significant finding is defined as more than one severity grade increase (worsening) from baseline in one or both eyes. If a pathology is recorded at a follow-up visit but not at baseline, the baseline will be imputed with the same pathology, with a grade of zero (none).

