8.2.8. Slit-lamp Biomicroscopy

Biomicroscopic examinations will be performed using a slit-lamp. The examinations will include evaluation of the condition of the eyelids, conjunctiva, cornea, anterior chamber, and iris/pupil.

AGN-190584

Eyelid/Eyelid Margins/Lashes:Edema

0	(None)	=	No edema
+0.5	(Trace)	=	Localized, minimal (trace) swelling
+1	(Mild)	=	Localized, mild swelling
+2	(Moderate)	=	Diffuse, moderate swelling
+3	(Severe)	=	Diffuse, severe swelling

Erythema

0	(None)	=	No erythema
+0.5	(Trace)	=	Localized, minimal (trace) flush reddish color
+1	(Mild)	=	Localized, mild, flush reddish color
+2	(Moderate)	=	Diffuse reddish color encompassing the entire lid margin
+3	(Severe)	=	Deep diffuse reddish color of lid margins and superior and/or inferior eyelid

Conjunctiva (Bulbar):Hyperemia

0	(None)	=	No hyperemia
+0.5	(Trace)	=	Minimal (trace) flush, reddish color
+1	(Mild)	=	Mild flush, reddish color
+2	(Moderate)	=	Bright red color
+3	(Severe)	=	Deep, bright diffuse redness

Edema

0	(None)	=	No edema
+0.5	(Trace)	=	Localized, minimal (trace) swelling
+1	(Mild)	=	Localized, mild swelling
+2	(Moderate)	=	Diffuse, moderate swelling
+3	(Severe)	=	Diffuse, severe swelling

AGN-190584

Conjunctiva (Palpebral):Hyperemia

0	(None)	=	No hyperemia
+0.5	(Trace)	=	Minimal (trace) flush, reddish color
+1	(Mild)	=	Mild flush, reddish color
+2	(Moderate)	=	Bright red color
+3	(Severe)	=	Deep, bright diffuse redness

Edema

0	(None)	=	No edema
+0.5	(Trace)	=	Localized, minimal (trace) swelling
+1	(Mild)	=	Localized, mild swelling
+2	(Moderate)	=	Diffuse, moderate swelling
+3	(Severe)	=	Diffuse, severe swelling

Cornea:Edema

0	(None)	=	No edema
+0.5	(Trace)	=	Localized, minimal (trace) epithelial haze
+1	(Mild)	=	Dull glass appearance of epithelium that may include fine localized microcystic changes
+2	(Moderate)	=	Dull glass appearance of the epithelium with large number of cystic changes with or without stromal edema
+3	(Severe)	=	Epithelial bullae and/or stromal edema, localized or diffuse, with or without stromal striae

Superficial Punctate Keratopathy

0	=	No superficial punctate keratopathy
+0.5	=	Trace
+1	=	Mild
+2	=	Moderate
+3	=	Severe

Anterior Chamber:

The anterior chamber will be evaluated for pathology. If pathology is present, it will be described.

██████████
AGN-190584

Iris/Pupil:

The iris/pupil will be evaluated for pathology. If pathology is present, it will be described.

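### The SAP's biomicroscopy rule needs a grade change, but the protocol records anterior chamber and iris/pupil pathology only as descriptions; for graded structures the rule is ambiguous and cannot flag an eye at moderate at baseline

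*SAP*

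**What the plan says.** Protocol 8.2.8 lists the eyelids, conjunctiva, cornea, anterior chamber and iris/pupil as the structures examined. Eyelid, conjunctival and corneal findings each get a scale of 0, +0.5, +1, +2, +3. The other two structures get no scale. For one the instruction is "The anterior chamber will be evaluated for pathology. If pathology is present, it will be described"; for the other, "The iris/pupil will be evaluated for pathology. If pathology is present, it will be described".

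SAP 5.6.9 treats the examination as graded throughout: "Observations for the examination will be graded on a 5-point scale (0=none, 0.5=trace, 1=mild, 2=moderate, 3=severe) except for the anterior chamber". The anterior chamber has its own scales, for cells ("in cells: 0=0 cells, +0.5=1-5 cells, +1=6-15 cells, +2=16-25 cells, +3=26-50 cells, and +4=>50 cells") and for flare ("in flare: 0=none, +1=faint, +2=moderate, +3= marked and +4=intense"). The SAP's list of structures is open-ended ("including but not limited to lids/lashes, conjunctiva, cornea, and anterior chamber") and does not name the iris/pupil.

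The table described in that section holds clinically significant findings only, by category, timepoint and arm. The criterion is: "A clinically significant finding is defined as more than one severity grade increase (worsening) from baseline in one or both eyes". Pathology seen at follow-up but not at baseline is given a baseline grade of zero.

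SAP Appendix 2, which lists changes from the protocol's planned analyses, mentions only the primary endpoint.

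**The concern.** The two documents disagree on whether the anterior chamber is graded, and the counting rule works only if it is. Protocol 2.2 says the drug constricts the iris sphincter and contracts the ciliary muscle, and exclusion criteria 4.04 and 4.05 screen out narrow angles, iris trauma and abnormal pupils. The structures without a protocol grade are therefore ones the protocol itself treats as relevant. An empty row for them could be read as no findings when it means that the rule could not classify what was recorded.

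For the graded structures there are two further problems. The scale has a half-step (trace), so one grade can mean one numeric unit or one category. And the top of the scale leaves no room for a rise of more than one grade from moderate.

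**Working it through.** The plan gives no figure to reproduce here. The check sets the two sections side by side and then lists what the rule counts.

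**1. Findings without a grade.** The rule needs (follow-up grade − baseline grade) > 1. For a new anterior chamber or iris/pupil finding recorded as protocol 8.2.8 states, the SAP sets the baseline to 0, but the follow-up grade does not exist. The difference is undefined. The imputation supplies the wrong one of the two values. For a described finding present at both visits, both values are missing.

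**2. New findings if the SAP's grades are collected** (baseline 0):

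| Scale (SAP 5.6.9) | Counted, grade = unit | Counted, grade = category |
|---|---|---|
| 5-point: 0, 0.5, 1, 2, 3 | 2, 3 | 1, 2, 3 |
| Cells: 0, 0.5, 1, 2, 3, 4 | 2, 3, 4 | 1, 2, 3, 4 |
| Flare: 0, 1, 2, 3, 4 | 2, 3, 4 | 2, 3, 4 |

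With cell and flare grades in the database, new anterior chamber findings of +2 or more count on either reading.

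**3. All worsenings on the 5-point scale.** Five levels give 5 × 4 / 2 = 10 upward transitions:

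| From → to | Units | Categories | Unit reading (> 1) | Category reading (> 1) |
|---|---|---|---|---|
| 0 → 0.5 | 0.5 | 1 | no | no |
| 0 → 1 | 1 | 2 | no | **yes** |
| 0 → 2 | 2 | 3 | yes | yes |
| 0 → 3 | 3 | 4 | yes | yes |
| 0.5 → 1 | 0.5 | 1 | no | no |
| 0.5 → 2 | 1.5 | 2 | yes | yes |
| 0.5 → 3 | 2.5 | 3 | yes | yes |
| 1 → 2 | 1 | 1 | no | no |
| 1 → 3 | 2 | 2 | yes | yes |
| 2 → 3 | 1 | 1 | no | no |
| **Counted** | | | **5 of 10** | **6 of 10** |

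The readings differ only for 0 → 1, a new mild finding. From a baseline of 2 the only possible worsening is to 3, which is one unit and one category, so it is never counted. These are counts of possible transitions, not of expected participants; the documents give no frequencies.

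**The case against.** The strongest reply is that the SAP's scales show its authors expected graded data. It spells out cell and flare grades, its 5-point scale nominally covers everything else, including the iris/pupil, and a baseline grade of zero for newly seen pathology makes sense only if recorded pathology carries a grade. An instruction to describe pathology does not rule out a severity field on the case report form. The case report form and Procedure Manual are not available, and parts of the protocol are blacked out. This stands, and it limits the claim. A reader might infer that anterior chamber or iris/pupil pathology can never be counted, or that exactly 0% of it qualifies. The documents do not support that, because grades may be captured somewhere not visible. What they do show is an undeclared conflict between the two sections and no rule for an ungraded finding.

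Second, other reporting exists. Under Protocol Appendix 2, a new condition detected after dosing or an increase in the intensity of an existing one is an adverse event, and SAP 5.6.2 tabulates and lists treatment-emergent events. SAP 5.1 codes biomicroscopy in MedDRA, and the SAP Introduction places table specifications in a separate document. So a reader should not conclude that such findings are hidden from the trial's safety reporting, or that this is the only biomicroscopy table planned. The adverse event route is only a partial backstop, however. It depends on the investigator reporting the finding, and Appendix 2 leaves out abnormal assessments tied to the underlying disease unless judged more severe than expected. Coding gives a finding a name, but it does not get an ungraded finding past the threshold in 5.6.9.

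Third, a threshold above one grade is meant to exclude one-step changes, and eyes at moderate at baseline may be few, since criterion 4.09 excludes clinically significant abnormal ophthalmic findings. Both points are fair for 1 → 2. They do not settle 0 → 1, and they do not alter the fact that worsening from moderate to severe cannot meet the definition.

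**Conclusion.** The concern holds for the stated rule applied to the stated collection. Under Protocol 8.2.8, new or worsened anterior chamber and iris/pupil pathology has no defined outcome in the SAP 5.6.9 table, and the baseline imputation does not repair this. If cell and flare grades are in fact collected, the anterior chamber gap closes for grades of +2 or more. The iris/pupil gap then remains unless a grade is collected there too, since neither document gives that structure its own scale.

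For graded structures, 5 or 6 of the 10 possible worsenings count depending on the reading, and an eye at moderate at baseline cannot be flagged. The effect is confined to descriptive biomicroscopy reporting. No hypothesis test is affected, and adverse event reporting is separate. The conclusion assumes only that sites record what Protocol 8.2.8 describes; it makes no claim about how many participants are involved.

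**What to change.** In SAP 5.6.9:

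1. Reconcile the anterior chamber scale with Protocol 8.2.8 and with the data actually collected, and record the difference in SAP Appendix 2 if one remains. Keep the cell and flare grades if they are captured; dropping them outright could discard graded safety data.
2. For any finding recorded without a grade (anterior chamber, iris/pupil), tabulate by arm the pathology newly recorded, or described as worse than baseline, in either eye.
3. State whether more than one grade means categories or numeric units.
4. For graded structures, add a descriptive shift table of baseline grade by worst post-baseline grade per arm, so that moderate-to-severe changes are visible.

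This needs SAP wording and one or two more descriptive tables, with no new data collection. The downside is that some minor findings will be tabulated.

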**5.6.10. Near Contrast Sensitivity**

Near contrast sensitivity assessment is conducted under photopic conditions. A Pelli-Robson contrast sensitivity chart is used. The logarithmic contrast sensitivity value of the last triplet of which at least 2 letters are correct read is marked as contrast sensitivity. Descriptive statistics for near contrast sensitivity and changes from baseline at each assessment timepoint will be presented by treatment group.

AGN-190584

## **5.8. Interim Analyses**

No interim analysis is planned for this study.

### **5.8.1. Data Monitoring Committee**

Data monitoring committee is not required for this study.

AGN-190584

**6. Supporting Documentation**

AGN-190584

**6.1. Appendix 1 List of Abbreviations**

AE	adverse event
ANCOVA	analysis of covariance
bpm	beats per minute
CDF	cumulative distribution function
CDVA	corrected distance visual acuity
DCIVA	distance-corrected intermediate visual acuity
DCNVA	distance-corrected near visual acuity
eCRF	electronic case report form
ID	identification
IOP	intraocular pressure
ITT	intent-to-treat
IxRS	interactive electronic response system
MAR	missing at random
MedDRA	Medical Dictionary for Regulatory Activities
mm Hg	millimeters of mercury
MMRM	mixed model repeated measure
MNAR	missing not at random
NEI VFQ-25	National Eye Institute Visual Function Questionnaire 25
NVPTQ	Near Vision Presbyopia Task-based Questionnaire
OD	right eye
OS	left eye
OSDI	Ocular Surface Disease Index
PCS	potentially clinically significant

PICQ Presbyopia Impact and Coping Questionnaire

PRO patient reported outcomes

[figure not shown]
AGN-190584

PT	preferred term
SAE	serious adverse event
SAP	statistical analysis plan
SD	standard deviation
SOC	system organ class
TEAE	treatment-emergent adverse event
TESAE	treatment-emergent serious adverse event
VAS	visual analog scale
WHO DDE	World Health Organization Drug Dictionary Enhanced
WOCBP	women of childbearing potential

AGN-190584

**6.2. Appendix 2: Changes to Protocol-Planned Analyses**

The primary efficacy endpoint will be the proportion of participants gaining 3 lines or more from baseline in mesopic, high contrast, binocular DCNVA without losing more than 5-letters of mesopic, high contrast, binocular CDVA with the same refractive correction at Day 30, Hour 3.

AGN-190584

### **6.3. Appendix 3: Supporting Study Information**

#### **6.3.1. Demographics**

Demographic parameters (age; age groups of  $\leq 50$  years and  $> 50$  years; sex; race; ethnicity) will be summarized descriptively by treatment group for the ITT populations.

#### **6.3.2. Baseline Characteristics**

Baseline binocular DCNVA (2 groups: 20/40 to 20/60 inclusively, and worse than 20/60), iris color (brown and non-brown), and emmetropes/non-emmetropes will be summarized descriptively with frequency and percentage by treatment group for the ITT population.

#### **6.3.3. Protocol Deviations**

Unique participants reporting significant protocol deviations will be summarized in total and by treatment group for all randomized participants.

#### **6.3.4. Medical History**

Medical and surgical history will be summarized by treatment group for the Safety Population. Medical history includes prior medical history (prior to Day 1, first dose date) and still ongoing.

#### **6.3.5. Ophthalmic Medical History**

Ophthalmic medical and surgical history will be summarized by treatment group for the Safety Population. Ophthalmic medical history includes prior medical history (prior to Day 1, first dose date) and still ongoing.

#### **6.3.6. Prior/Concomitant medications**

*Prior medication* is defined as any medications taken prior to the start of study intervention.

*Concomitant medication* is defined as any medication taken on or after the start of study intervention regardless of the start date of the medication.

The number and percentage of participants with prior and concomitant medication use will be summarized by treatment group and Anatomical Therapeutic Chemical code for the safety population. If a participant took a specific medication multiple times or took multiple medications within the same therapeutic class, the participant will be counted only once for the coded drug name or therapeutic class. Formulations (including salts, esters, etc.) containing the same active ingredient will be pooled under the coded drug name of the base compound. Medications containing multiple active ingredients of different coded drug names will be

AGN-190584

reviewed during the course of the study and may be pooled under a single coded drug name for analyses. No statistical comparisons will be performed.

AGN-190584

## 6.4. Appendix 4: PRO Scoring Algorithm

### 6.4.1. NVPTQ Performance Domain Score

To account for the impact of squinting on performance, the responses to the pair of performance and squinting items on each task is combined into a new testlet variable informed by a series of item response theory models. For performance and squinting, this new testlet variable is created by combining all possible response categories according to Table 1.

**Table 1 Testlet variable values based on combining performance item responses and squinting item responses**

Squinting \ Performance	Yes, but I still could not read any of the text (2)	Yes, and squinting helped me read some or all of the text (1)	No, I did not squint (0)
I could not read any of the text due to problems seeing up close (0)	0	0	0
Poor (1)		0	1
Fair (2)		1	2
Good (3)		2	3
Very Good (4)		3	4
Excellent (5)		4	5

Note. The values in parentheses are the raw values corresponding to the item response. These are the variable values in the ADaM datasets.

If the response to either the performance or squinting item within a task is missing, then the corresponding testlet is assigned a missing value. Because the four tasks are highly related, there is no limit on the number of missing testlet scores to be able to calculate the performance domain score. The performance domain score is calculated as the average of the non-missing testlet values as follows:

NVPTQ Performance Score = (Book testlet + Newspaper testlet + Menu testlet + Nutrition Label testlet) / (# testlets with non-missing responses)

AGN-190584

The NVPTQ Performance Score ranges from 0 to 5, with 0 corresponding to poorest performance and 5 corresponding to best performance. Thus, higher scores correspond to better outcomes. This algorithm puts the performance score on the original performance item response metric, which also ranges from 0 to 5, so the performance item responses can be referenced when interpreting the score. Individual-level score changes of 0.75 points or greater can be considered clinically meaningful; i.e., an individual whose NVPTQ Performance Score increases by at least 0.75 points from baseline can be considered a responder.

#### 6.4.2. NVPTQ Satisfaction Domain Score

To account for the impact of squinting on satisfaction, the responses to the pair of satisfaction and squinting items on each task is combined into a new testlet variable informed by a series of item response theory models. For satisfaction and squinting, this new testlet variable is created by combining all possible response categories according to Table 2.

**Table 2 Testlet variable values based on combining satisfaction item responses and squinting item responses**

Squinting \ Satisfaction	Yes, but I still could not read any of the text (2)	Yes, and squinting helped me read some or all of the text (1)	No, I did not squint (0)
Very dissatisfied (0)	0	0	0
Dissatisfied (1)		0	1
Neither satisfied nor dissatisfied (2)		1	2
Satisfied (3)		2	3
Very satisfied (4)		3	4

Note. The values in parentheses are the raw values corresponding to the item response. These are the variable values in the ADaM datasets.

If the response to either the satisfaction or squinting item within a task is missing, then the corresponding testlet is assigned a missing value. Because the four tasks are highly related, there is no limit on the number of missing testlet scores to be able to calculate the satisfaction domain score. The satisfaction domain score is calculated as the average of the non-missing testlet values as follows:

AGN-190584

NVPTQ Satisfaction Score = (Book testlet + Newspaper testlet + Menu testlet + Nutrition Label testlet) / (# testlets with non-missing responses)

The NVPTQ Satisfaction Score ranges from 0 to 4, with 0 corresponding to greatest dissatisfaction and 4 corresponding to greatest satisfaction. Thus, higher scores correspond to better outcomes. This algorithm puts the satisfaction score on the original satisfaction item response metric, which also ranges from 0 to 4, so the satisfaction item responses can be referenced when interpreting the score. Individual-level score changes of 1.00 points or greater can be considered clinically meaningful; i.e., an individual whose NVPTQ Satisfaction Score increases by at least 1.00 points from baseline can be considered a responder.

### 6.4.3. PICQ Coping Score

The coping domain consists of the following 8 items:

- Item 1: Normal-sized text
- Item 2: Small-sized text
- Item 3: Information on a computer
- Item 4: Information on a cell phone
- Item 5: Increase font size
- Item 6: Use glasses to read close
- Item 12: Hold reading materials farther out or closer
- Item 13: Squint to read

Each of these items includes response categories ranging from 0, corresponding to “Never”, to 4, corresponding to “All of the time.” Items 3, 4, 5, and 6 include additional response categories, labeled with values of 9 or 10, to indicate that the question is not applicable because the participant did not use the object being evaluated (e.g., “I did not use a computer over the past 7 days”) or because the participant did not have the opportunity to change his behavior (e.g., “I permanently increased the font size on my computer, tablet, or cell phone prior to the past 7 days”). Responses in these “not applicable” categories labeled 9 or 10 are assigned missing values.

Because of the similarity of the content of certain item pairs, two new testlet variables are created prior to scoring. The testlet variable for Item 1 and Item 2 is calculated by computing the mean of the non-missing responses to the two items. The testlet variable for Item 3 and Item 4 is calculated by computing the mean of the non-missing responses to the two items. If either item in the testlet pair has a missing value, the testlet value is assigned the value of the non-missing item. If both items in the testlet pair have missing values, then the testlet is assigned a missing value.

AGN-190584

Items 1&2 Testlet = (Item 1 + Item 2) / # non-missing responses to Item 1 and Item 2

Items 3&4 Testlet = (Item 3 + Item 4) / # non-missing responses to Item 3 and Item 4

After the testlet variables have been created, the coping domain score is calculated as the mean of the non-missing values to the coping testlets and single coping items. Because the coping items are well-related and internally consistent, and because missing data are expected for some items due to the “not applicable” response categories, there is no limit on the number of missing item responses to be able to calculate the coping domain score.

PICQ Coping Score = (Item 1&2 Testlet + Item 3&4 Testlet + Item 5 + Item 6 + Item 12 + Item 13) / # non-missing responses to the 6 components of the coping score

The PICQ Coping Score ranges from 0 to 4, with 0 corresponding to least amount of coping and 4 corresponding to the greatest amount of coping. Thus, higher scores correspond to poorer outcomes. This algorithm puts the coping score on the original item response metric, which also ranges from 0 to 4, so the coping item responses can be referenced when interpreting the score. Individual-level score changes of 1.00 points or greater can be considered clinically meaningful; i.e., an individual whose PICQ Coping Score decreases by at least 1.00 points from baseline can be considered a responder.

#### 6.4.4. PICQ Impact Score

The impacts domain consists of the following 6 items:

- Item 9: Rely on others
- Item 15: Rest eyes
- Item 16: Feel older
- Item 17: Feel self-conscious
- Item 19: Take longer to complete a task
- Item 20: Inconvenient

The first five impacts items include response categories ranging from 0, corresponding to “Never”, to 4, corresponding to “All of the time.” Item 20 uses response categories ranging from 0, corresponding to “Not at all”, to 4, corresponding to “Extremely.” Item 9 includes an additional response category, labeled with a value of 9, to indicate that the question is not applicable because the subject did not have the opportunity to experience the impact (i.e., “Never because I used or did something to help”). Responses in this “not applicable” category are assigned missing values.

Because of the similarity of the content of Item 16 and Item 17, a new testlet variable is created prior to scoring by computing the mean of the non-missing responses to the two items. If either

AGN-190584

item in the testlet pair has a missing value, the testlet is assigned the value of the non-missing item. If both items in the testlet pair have missing values, then the testlet is assigned a missing value.

Items 16&17 Testlet = (Item 16 + Item 17) /# non-missing responses to Item 16 and Item 17

After the testlet variable has been created, the impacts domain score is calculated as the mean of the non-missing values to the impacts testlet and single impacts items. Because the impacts items are well-related and internally consistent, and because missing data are expected for some items due to the “not applicable” response categories, there is no limit on the number of missing item responses to be able to calculate the impacts domain score.

PICQ Impacts Score = (Item 9 + Item 15 + Items 16&17 Testlet + Item 19 + Item 20) /# non-missing responses to the 5 components of the impacts score

The PICQ Impacts Score ranges from 0 to 4, with 0 corresponding to least amount of impacts and 4 corresponding to the greatest amount of impacts. Thus, higher scores correspond to poorer outcomes. This algorithm puts the impacts score on the original item response metric, which also ranges from 0 to 4, so the impacts item responses can be referenced when interpreting the score. Individual-level score changes of 1.00 points or greater can be considered clinically meaningful; i.e., an individual whose PICQ Impacts Score decreases by at least 1.00 points from baseline can be considered a responder.

